6.7.7 Missing Start and Stop Dates for Adverse Events

Start date:

- If start date is completely missing, start date is set to date of first dose.

- If (year is present, and month and day are missing) or (year and day are present, and month is missing):
 - If year = year of first dose, then set month and day to month and day of first dose.
 - If year < year of first dose, then set month and day to December 31st.
 - If year > year of first dose, then set month and day to January 1st.
- If month and year are present and day is missing:
 - If year = year of first dose and
 - If month = month of first dose, then set day to day of first dose date.
 - If month < month of first dose, then set day to last day of month.
 - If month > month of first dose, then set day to 1st day of month.
 - If year < year of first dose, then set day to last day of month.
 - If year > year of first dose, then set day to 1st day of month.

Stop date:

If the outcome of the AE was ongoing or unknown, then the rules outlined below will not be applied.

- If stop date is completely missing, stop date is set to date of study discontinuation.
- If (year is present, and month and day are missing) or (year and day are present, and month is missing):
 - If year = year of study discontinuation, then set month and day to month and day of study discontinuation.
 - If year < year of study discontinuation, then set month and day to December 31st.
 - If year > year of study discontinuation, then set month and day to December 31st.
- If month and year are present and day is missing:
 - If year = year of study discontinuation and
 - If month = month of study discontinuation, then set day to day of study discontinuation date.
 - If month < month of study discontinuation, then set day to last day of month.
 - If month > month of study discontinuation, then set day to last day of month.
 - If year < year of study discontinuation, then set day to last day of month.
 - If year > year of study discontinuation, then set day to last day of month.

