10.2 Study Procedures

10.2.1 Visit 1- Screening Visit (Day -21 to -1)

- Informed Consent
- Inclusion/Exclusion Criteria
- Demographics
- Medical History
- Concomitant and Prohibited Therapies review and documentation
- Physical examination
- Collection of Vital Signs
- Urine pregnancy test for WOCBP
- Venipuncture for Laboratory Assessment & Urinalysis
- Investigator's Global Assessment [IGA]
- Clinician's Erythema Assessment [CEA]
- Skindex-16
- Patient Self-Assessment (PSA)
- Fitzpatrick skin type
- Start AE collection and assessment

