12.4 Adverse Event Collection Period

Adverse Event Collection Period starts with the Screening visit once the ICF has been signed through the follow-up visit (week 12). Any AE/SAE prior to the Screening visit will be considered past medical history (PMH).

SAE(s) that are observed or spontaneously reported during the subject's participation in the trial will be captured and monitored until the Investigator deems the event to be chronic or not clinically significant or the subject to be stable.

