6.7.6 Safety Parameters

Safety and tolerability endpoints will consist of all adverse events (AEs) reported during the study duration from the date of randomization through Week 12 (End of Study Visit).

Specific AEs are defined below.

Treatment-Emergent Adverse Events (TEAE): Any AE with onset after the first dose of study medication through 56 days after the last dose of study medication.

Serious Adverse Event (SAE): An AE occurring at any dose that results in any of the following outcomes: death, a life-threatening AE, in-patient hospitalization or prolongation of existing hospitalization, a persistent or significant disability/incapacity, or a congenital anomaly/birth defect.

Associated with Use of the Study Drug: There is a reasonable possibility that the experience may have been caused by the study drug. If the Investigator does not know whether or not study drug caused the event, then the event will be handled as “related to study drug” for reporting purposes. The determination of whether an AE is related to study drug is as follows:

- Related: The AE has a missing, unknown, possible, probable or definite relationship to the study medication.
- Not related: The AE is unlikely or definitely unrelated to the study drug.

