8.2.1 Primary Safety Endpoint

Assess the safety and tolerability of B244 applied twice daily to the face for 8 weeks in subjects with mild to moderate rosacea.

The reporting of safety data is descriptive and will include all subjects who receive at least one dose of investigational product. The variables for safety endpoints are number of subjects with AEs, SAEs, vital signs measurements, clinical chemistry and hematology. AEs will be summarized based on the frequency of AEs and their severity for all treated subjects. All AEs will be coded using Medical Dictionary for Regulatory Activities (MedDRA) and summarized by treatment group. Data will be summarized using preferred term and primary system organ class.

If a subject experiences multiple events that map to a single preferred term, the greatest severity and strongest Investigator assessment of relation to investigational product will be assigned to the preferred term for the appropriate summaries. Should an event have a missing severity or relationship, it will be classified as having the highest severity and/or strongest relationship to investigational product.

Summaries of AEs will include any AEs reported beginning with the first dose of investigational product on Day 1. The occurrence of adverse events will be summarized by treatment group using preferred terms, system organ classifications, and severity. Separate summaries of serious adverse events, adverse events related to investigational product, and events leading to the discontinuation of investigational product will be generated. All adverse events reported will be listed for individual subjects showing both verbatim and preferred terms.

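### SAP 6.7.7 can impute an adverse event's onset to the first-dose date even when its recorded stop date shows that it ended before dosing; the rule is wrong as written, but few if any events should be affected.

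*SAP*

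**What the plan says.** SAP v2.0 section 6.7.7 sends an incomplete AE start date to the first-dose date in three situations:

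- Start completely missing: "If start date is completely missing, start date is set to date of first dose".
- Month missing, year known: "If year = year of first dose, then set month and day to month and day of first dose".
- Only the day missing, in the first-dose year: "If month = month of first dose, then set day to day of first dose date".

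Other partial dates stay on the side of dosing that the known part implies. For example, for an earlier year: "If year < year of first dose, then set month and day to December 31st". The stop-date rules in the same section fill in missing stop dates, but do not compare them with the start. SAP v1 has the same text.

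AE collection begins before dosing (protocol 12.4: "Adverse Event Collection Period starts with the Screening visit once the ICF has been signed through the follow-up visit (week 12"). Protocol 10.2.1 places Screening at Day -21 to Day -1.

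Two statements define what counts as on treatment. SAP 8.2.1: "Summaries of AEs will include any AEs reported beginning with the first dose of investigational product on Day 1". SAP 6.7.6, defining a TEAE: "Any AE with onset after the first dose of study medication through 56 days after the last dose of study medication".

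**The concern.** Assigning an unknown onset to the first-dose date is a normal conservative convention when nothing shows whether the event began before or after exposure. It is not defensible when the record itself settles the matter. If the stop date is known and precedes the first dose, the event cannot have begun on treatment. The rule then overrides known data and produces a start later than the stop.

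The primary objective is safety and tolerability, and the safety endpoint is the AE record. An event known to have ended before any product was applied should not be counted there as on treatment.

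**Working it through.** There is no planned figure to reproduce, so the check applies the rule as written.

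**One record.** Take an assumed first dose of 25 March. Day -21 is 4 March, so an event that stopped on 15 March (Day -10) can lie wholly within the AE collection period. With the start completely missing, 6.7.7 gives an onset of 25 March. Imputed onset minus recorded stop is 25 − 15 = 10 days, in the wrong direction.

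**All screening-only events.** The three branches were applied to every pair of true start and recorded stop with both dates between Day -21 and Day -1. That is 21 × 22 / 2 = 231 pairs for each first-dose date. First-dose dates ran daily from 1 July 2018 to 30 June 2019 (365 dates, assumed only to exercise the rule), giving 231 × 365 = 84,315 cases.

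| What is known of the start | Imputed onset after recorded stop | Imputed onset on first-dose date |
|---|---|---|
| Nothing | 100% | 100% |
| Year only | 97.9% | 96.1% |
| Month and year | 74.8% | 52.9% |

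The year-only exceptions come from screening periods that cross New Year. In no case is the imputed onset strictly later than the first-dose date, which matters for the TEAE question below.

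**Which displays are reached.** Under 8.2.1 the window opens with the first dose on Day 1, so an onset on that date is inside it. Under 6.7.6 the onset must come after the first dose, so on a strict comparison of dates an onset equal to the first-dose date is outside. Tables 14.3.1 to 14.3.1.3 and Listing 16.2.3.1 are all TEAE displays, so the two sections give different answers for them.

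**How many events.** The documents give neither an expected AE rate for this trial nor a rate of incomplete dates, so this step rests on assumptions. Let *g* be the days from Screening to first dose, uniform on 1 to 21. Let onset be uniform from Screening to Day 84, and duration exponential with mean *m* days.

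- P(onset before dosing) = average over *g* of g / (g + 84) ≈ 11%.
- P(onset and stop before dosing) = average over *g* of [g − m(1 − e^(−g/m))] / (g + 84) = 8.5%, 6.1% and 4.0% for *m* = 3, 7 and 14.

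So about 4% to 8.5% of AEs with a completely missing start would be misplaced, provided that their stop dates are recorded.

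To turn this into a count, borrow the 16% of subjects with a TEAE in the sponsor's completed blood-pressure study (protocol 1.2.1). With 130 subjects, 130 × 0.16 = 20.8 subjects.

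- One AE each, 5% with missing onset: 20.8 × 0.05 × 0.04 = 0.04, up to 20.8 × 0.05 × 0.085 = 0.09 events.
- Two AEs each, 10% with missing onset: 41.6 × 0.10 × 0.04 = 0.17, up to 41.6 × 0.10 × 0.085 = 0.35 events.

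Both scenarios give an expected count below one event in the whole trial.

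**The case against.** The best defence is that the triggering record is rare. Protocol section 12 requires the date of onset, subjects are asked directly about AEs from Screening (11.2.1), Baseline follows within 21 days, and anything before Screening is past medical history (12.4). The record needs a known stop and an incomplete start inside about three weeks. The SAP also rests on a Data Management Plan that is not available here, so date queries may remove most cases. All of this stands and limits the size. It does not correct the rule, which exists for the dates that stay incomplete.

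A second defence is that the TEAE definition keeps first-dose-date onsets out of the tables. On a strict date comparison it does. But that reading would also exclude events whose timing is truly unknown, which defeats the purpose of imputing to the first dose, and it conflicts with 8.2.1. It is a reason to reconcile the sections.

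A reader might infer several stronger consequences that the documents do not support:

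- *Washout flares of rosacea counted as on treatment.* Protocol 12.1.1 records new or worsening rosacea as an AE when the investigator attributes it to the product rather than the disease. A flare that ended before dosing would not generally qualify.
- *Events attributed to B244 or vehicle.* Relatedness is the investigator's rating (protocol 12.3), not a function of the imputed date. The default to related applies only if that rating is missing or unknown as well.
- *Dilution of a true difference between arms.* Equal additions to both arms leave the expected difference in event counts unchanged. If a fraction *q* of subjects gains a spurious event independently of any real one, the difference in subject incidence is multiplied by (1 − q). At the upper figure above, q = 0.35 / 130 ≈ 0.003. Safety reporting is descriptive, so no test loses power.
- *Distorted duration results.* No planned safety table reports AE duration.
- *Every year-only onset moved on treatment.* Only those in the first-dose year are. An earlier year goes to 31 December and stays before dosing.

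**Conclusion.** The rule is wrong as written. Whenever the start is completely missing and the recorded stop precedes the first dose, 6.7.7 gives an onset after the event ended. For year-only and month-and-year starts it does so in most of the cases enumerated. The resulting first-dose-date onset lies inside the 8.2.1 window; entry into the TEAE tables is undetermined until 6.7.6 and 8.2.1 agree.

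The practical effect is probably under one event (0.04 to 0.35 in the scenarios shown), and it can occur in both arms. That size depends on an AE frequency borrowed from another indication, assumed missing-date rates of 5% to 10%, a uniform hazard, and recorded stop dates. The fault in the rule needs none of these assumptions. This is a desirable correction and does not threaten the trial's conclusions.

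**What to change.** Add to SAP 6.7.7:

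> *The imputed start date is the earlier of the date given by the rules above and the recorded stop date (or the latest date consistent with a partial stop date). An AE whose stop date is before the first dose is not treatment-emergent.*

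This is a cap and not a replacement. Simply setting the start to the stop date could overwrite a known earlier month or year, whereas taking the earlier date keeps it. For every screening-only event enumerated above, the capped start is no later than the recorded stop and so falls before the first dose. Events with no usable stop date keep the conservative default.

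Then state in both 6.7.6 and 8.2.1 whether an onset imputed to the first-dose date counts as treatment-emergent, so that the text and the TEAE tables use one window.

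The cost is a few lines of SAP text and one programming condition. No data collection changes.

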7 DATA ANALYSES

The data analysis will be conducted on all participant data when the trial ends. Subjects will be pooled across all sites. Data will be presented by treatment group and overall. Categorical variables will be summarized by frequency distributions (number and percentages of subjects) and continuous variables will be summarized by descriptive statistics (mean, standard deviation, etc.).

Adverse events will be summarized by treatment group using the Medical Dictionary for Regulatory Activities (MedDRA) system organ class and preferred term. Separate tabulations will be produced for all treatment-emergent AEs (TEAEs), treatment-related AEs (those considered by the Investigator as at least possibly drug related), SAEs, discontinuations due to AEs, and AEs Grade 3 severity. By-subject listings will be provided for any deaths, SAEs, and AEs leading to discontinuation.

Descriptive statistics for each treatment group will be provided for clinical laboratory values (e.g., hematology, serum chemistry, and urinalysis) and vital signs data, presented as both actual values and changes from baseline relative to each on-study evaluation. Abnormal clinical laboratory values will be listed.

All data will be provided in by-subject listings.

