6.5 Treatment Assignment (Randomization)

Randomization will be performed using an Interactive Web Response System (IWRS) at the time the subject has met all eligibility criteria and is ready for enrollment. Subjects will be randomized in a 1:1 ratio to receive either B244 or vehicle and will be stratified by site.

Interactive Web Response System (IWRS) will assign subjects to the treatment arm and specify the kit number to be dispensed.

The randomization scheme will be generated and held by the independent third party throughout the conduct of the study and will not be available to the Sponsor, Investigator, or study staff, or to clinical staff who could have an impact on the outcome of the study.

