10 STUDY PROCEDURES AND SCHEDULE OF STUDY ACTIVITIES

The following sections describe the procedures to be completed during the study. Subjects are to be assessed by the same Investigator or site personnel whenever possible.

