6.7.4 Handling of Missing Data & Sensitivity Analysis

For the primary and secondary analysis no missing values will be imputed. A sensitivity analysis will be performed by Multiple Imputation Regression Analysis using the following factors: treatment, age, gender, race, baseline IGA, baseline CEA, baseline PSA, smokers/non-smokers and the results of the same variable from previous visits.

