8.3 Efficacy Analysis

All efficacy endpoints are exploratory endpoints.

Assessment of Superiority:

- IGA treatment success, defined as “clear” or “almost clear” with a 2-grade improvement in IGA score from baseline to the end of treatment (Week 8).
- CEA treatment success, defined as “clear” or “almost clear” with a 2-grade improvement in CEA score from baseline to the end of treatment (Week 8).

Superiority will be based on the proportion of subjects for whom treatment was successful. The comparison will be through a continuity-corrected Z-tests. The Evaluable Period for the outcome variables will be weeks 1, 4, 8 and 12. The superiority of the drug over the vehicle will be tested at week 8 based on the probability of

improvement from baseline with a continuity-corrected Z-tests comparing the change from baseline of treatments vs Placebo. For all other evaluable periods, descriptive statistics for the change from baseline will be shown.

The null and alternative statistical hypotheses for the primary effectiveness endpoints are given by:

(*H*₀): The null hypothesis is that the probability of improving (baseline to week 8) with drug T (*Pr*_T) is less than or equal to the probability of improving with vehicle (*Pr*_V).

$$H_0: Pr_T - Pr_V \leq 0; Pr_T$$

(*H*_a): The alternative hypothesis is that the probability of improving with drug T (*Pr*_T) is greater than to the probability of improving with vehicle (*Pr*_V).

$$H_a: Pr_T > Pr_V; Pr_T - Pr_V > 0$$

For testing the superiority, the following SAS code will be used:

```
proc freq data = dataset;
  tables treat*outcome/riskdiff (equal);
run;
```

- Change of Skindex 16 patient reported outcome from Baseline to Week 1, Week 4, Week 8 and Week 12

The change from baseline score of Skindex-16 will be compared among treatments at Week 12 using an ANOVA, to test the Skindex 16 score change from Baseline to Week 12 for the two treatments. Also, descriptive stats will be used to assess the change from Baseline to Week 1, 4, 8 & 12.

- Change of IGA score at Baseline to Week 1, Week 4, Week 8 and Week 12.
- Change of CEA score at Baseline to Week 1, Week 4, Week 8 and Week 12.
- Change of PSA score at Baseline to Week 1, Week 4, Week 8 and Week 12.

Descriptive stats will be used to show the change from Baseline to Week 1, 4, 8 & 12.

- Supplemental Analysis

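### Randomization is stratified by site, but the Week 8 IGA and CEA success tests pool the sites; a site-stratified test would match the design and change power only slightly, in either direction

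*SAP*

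**What the plan says.** Protocol 6.5 names one stratification factor: "Subjects will be randomized in a 1:1 ratio to receive either B244 or vehicle and will be stratified by site". It gives no block size. SAP section 7, in both versions, then says "Subjects will be pooled across all sites".

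For Week 8 IGA and CEA treatment success, SAP 8.3 says "The comparison will be through a continuity-corrected Z-tests". Its code requests a two-way table, "tables treat*outcome/riskdiff (equal", closing the bracket there: no site stratum and no correction option. No section gives a stratified or site-adjusted efficacy analysis or explains the omission. The only display titled by site is the disposition listing (16.2.1.1).

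The imputation factors in SAP 6.7.4, repeated in 8.4, are "treatment, age, gender, race, baseline IGA, baseline CEA, baseline PSA, smokers/non-smokers and the results of the same variable from previous visits". Site is not among them.

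SAP 8.3 also states: "All efficacy endpoints are exploratory endpoints".

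**The concern.** An analysis normally conditions on the factor that the randomization balanced. If it does not, and that factor predicts outcome, between-site variation stays in the standard error of a comparison that was largely protected from it. The test then becomes somewhat conservative.

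Site could plausibly matter here. IGA and CEA are investigator ratings, and Protocol section 10 says "Subjects are to be assessed by the same Investigator or site personnel whenever possible", so any difference between raters would follow site. The documents do not show that such differences exist.

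At stake are a small amount of power, an error rate closer to nominal, and a method fixed before unblinding.

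**Working it through.** **Inputs from the documents.** 33% vs 10%, two-sided 5%, 80% power, 104 subjects (SAP 8.1); 130 enrolled, 20% dropout (SAP 4.3); about 8 sites (SAP 2.1, Protocol 4.2) or about 9 (SAP 4.3). SAP 8.1 does not define the IGA response it powers for; it is taken here as the success endpoint.

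**Inputs assumed.** Site effects normal on the logit scale, SD 0 to 1.0, with marginal rates held fixed; permuted blocks of 4 within site; four site layouts (8 or 9 sites, equal or unequal); random dropout with completers analysed, because SAP 6.7.4 says "For the primary and secondary analysis no missing values will be imputed".

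**The plan's own figure.** The dropout step reproduces: 104/0.8 = 130. The pooled-variance formula, with mean rate 0.215, gives

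n per arm = [1.96·√(2·0.215·0.785) + 0.8416·√(0.33·0.67 + 0.10·0.90)]² / 0.23² = (1.1387 + 0.4694)² / 0.0529 = 48.9,

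so 49 per arm, or 98 in total. The continuity-corrected version gives 116. Neither equals 104, but the comparison below does not depend on this.

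**Why pooling is conservative.** With arms balanced within site, the true variance of the risk difference depends on the mean of p_s(1 − p_s) over sites. The pooled Z uses p̄(1 − p̄), which is larger by Var(p_s). As an illustration under the null, put half the sites at 2.75% and half at 17.25% (mean 10%, log-odds 2.0 apart, so SD 1.0).

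- Pooled variance term: 0.10·0.90 = 0.0900.
- Within-site term: (0.0275·0.9725 + 0.1725·0.8275)/2 = 0.0847.
- Ratio 0.942; effective critical value 1.96/√0.942 = 2.02; two-sided type I error about 4.3%.

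**Tests compared.** CMH statistic: [Σ(a_s − n1s·m_s/n_s)]² / Σ[n1s·n2s·m_s(n_s − m_s)/(n_s²(n_s − 1))], where site s has n1s and n2s subjects per arm, n_s in total, m_s successes and a_s active-arm successes. The comparators are the unstratified pooled Z and Wald tests; the documents do not say which one the printed code is meant to run. There were 200,000 simulated trials per scenario.

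Power difference in percentage points, all tests uncorrected, range over the four layouts:

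| Site SD | CMH minus pooled Z | CMH minus Wald |
|---|---|---|
| 0 | -0.9 to -1.4 | -1.8 to -2.3 |
| 0.5 | 0.0 to -0.5 | -0.9 to -1.4 |
| 0.7 | +0.3 to +0.8 | -0.1 to -0.6 |
| 1.0 | +1.6 to +2.1 | +0.8 to +1.3 |

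A separate simulation agreed on the overall ranges within 0.1 point. Part of Wald's advantage comes from its higher type I error (5.5–5.6% at 10%/10%, SD 0). With the correction on both sides, CMH minus pooled Z runs from about -1.8 to +2.7.

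**Type I error, uncorrected, SD 0 then SD 1.0.**

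- At 10%/10%: pooled Z 5.0–5.1%, then 4.3–4.4%; CMH 4.7–4.9% throughout.
- At 5%/5%: pooled Z 4.4%, then 3.6–3.7%; CMH 4.2–4.3%, then 3.8–4.0%. The two are about equally conservative.

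**Separating the continuity correction from site (8 equal sites).** Power at SD 0 / SD 1.0 is 76.5/76.9% for corrected pooled Z, 83.7/84.5% for uncorrected pooled Z, and 82.8/86.6% for uncorrected CMH. Going from the first to the last adds 6.3/9.7 points. Dropping the correction supplies 7.2/7.6 of that; stratifying supplies -0.9/+2.1.

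**Sensitivity.** Blocks of 2 or 6 move the differences by at most 0.4 points. At SD 1.5, CMH gains 4.1 to 4.8 points over pooled Z. With simple randomization within site, 104 subjects and SD 0, it loses 3.0 to 3.5. Merging sites with fewer than 8 randomized subjects recovers 0.2 to 0.5 points at SD 0.

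**The case against.** The best case for leaving the plan alone is that no harm is shown. Pooling is prespecified, all efficacy is exploratory, the primary objective is descriptive safety, and the sign of the power change depends on a site SD that the documents do not give. Success also requires a 2-grade change, usually scored by the same rater, so a constant rater offset partly cancels and a site SD near 1 may be too high. All of this stands. It makes the priority low but does not remove the mismatch.

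Three stronger readings are tempting, and the documents do not support them.

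- *A reader might infer that pooling invalidates the tests.* It does not. It causes no bias, and its effect on type I error is in the conservative direction.
- *A reader might credit stratification with 6 to 10 points of power*, by comparing uncorrected CMH with the corrected Z-test in the SAP text. Most of that gain comes from dropping the correction.
- *A reader might call the missing site term in the imputation model a defect of equal weight.* No benefit from adding it has been shown. Baseline and earlier-visit scores are already in that model, and Tables 14.2.10.1–14.2.10.3 analyse change scores rather than success.

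The completer assumption is also open to challenge. SAP 4.4 and 6.5.4 carry forward some lack-of-efficacy discontinuations as failures, and the simulation did not model this.

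**Conclusion.** The mismatch is real and minor. The case for a site-stratified test is agreement with the design and, at a 10% success rate, a type I error nearer nominal if sites differ (4.7–4.9% against about 4.3% at SD 1.0). It is not a promised gain in power. Under the stated assumptions the power change is -1.4 to +2.1 points against an uncorrected pooled Z and -2.3 to +1.3 against an uncorrected Wald test. Site SD, block size and site sizes are all assumed. At success rates near 5%, the type I advantage largely disappears.

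The continuity correction is a separate item with larger consequences. The SAP 8.3 text requires it and the printed code shows none. For the unstratified tests, removing it moves power from about 76–79% to 84–85%, across the stated 80%, and type I error from about 2% to 5%.

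**What to change.** 1. In SAP 8.3, test Week 8 IGA and CEA treatment success with a CMH test stratified by site (table request site*treat*outcome). Report the Mantel-Haenszel risk difference, Σw_s·d_s/Σw_s with w_s = n1s·n2s/n_s and d_s the risk difference in site s, with its 95% CI, in Tables 14.2.6.1–14.2.9.2.
2. Fix a small-site rule before unblinding, for example merging all sites with fewer than 8 randomized subjects into one stratum. SAP 2.1 and 4.3 should also agree on the number of sites.
3. Decide on the continuity correction as its own item, and state the decision explicitly for the stratified test.
4. Note that Tables 14.2.6.1–14.2.7.2 show the success endpoint only for subjects who entered at grade 2 or 3. Protocol 22.1.2 allows sponsor-approved eligibility deviations, and a fall from grade 4 to 2 would count there without being a success.
5. Optionally, add site to the imputation factors in 6.7.4 and 8.4, merged by the same rule. This adds up to 7 or 8 parameters, and its benefit is not shown.

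The cost is SAP wording and a small programming change, with no new data. If sites do not differ, it loses about 1 point of power against the pooled Z or about 2 against Wald. If the sponsor prefers to keep pooling, a sentence justifying that choice would also close the gap.
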